9.4. Prior and Concomitant Medications

Prior medications are defined as medications with stop dates occurring before the date of first administration of the study drug. Concomitant medications are defined as medications with start dates occurring before, on, or after the date of first administration of study drug and stopping after the first administration of study drug or continuing beyond that.

For the purpose of summarizing prior and concomitant medications, incomplete medication start and stop dates will be imputed as detailed in Section 6.8.2. Based on imputed start and stop dates, specifies the rules on how a medication is classified as either a prior or concomitant medication and how it will be assigned to a specific study drug.

Table 14: Rules for Prior and Concomitant Medications

Prior vs. Concomitant	Rules
Prior	Stop date was before the first administration of study drug.
Concomitant	1. Stop date was on or after the first administration of study drug.
	2. Or stop date was missing.
	3. Or both start and stop dates were missing.

All medications are coded using the World Health Organization Drug Dictionary (WHO-DD) version March 2017 – C format. WHO-DD ATC Class Level 1, WHO-DD ATC Class Level 2 and preferred term (PT) will be used to summarize the data by treatment.

9.5. Clinical Laboratory Data

No blood samples were collected for hematology and serum biochemistry tests.

Urine samples were collected for urine pregnancy tests. Urine pregnancy tests were done at all study visits. No tables reporting urine pregnancy test results will be produced. However, a data listing reporting urine pregnancy test results will be produced.

9.6. Vital Signs

The following vital sign parameters will be summarized by visit and treatment group:

- Diastolic Blood Pressure (mm Hg)
- Systolic Blood Pressure (mm Hg)
- Pulse Rate (beats/min)

In general, if multiple results are reported within the given analysis visit window for the same parameter, the mean of the results will be used for summary statistics except for baseline, for which the last assessment will be used.

For all vital sign parameter, the continuous results will be summarized using descriptive statistics by visit and treatment group. The summary statistics are n, mean, median, SD, minimum and maximum. Boxplots for vital signs versus time by treatment for all time points will also be generated. Boxplots will display Baseline, Day 28, Day 56 and Day 84 assessments.

Changes from baseline will also be summarized by visit and treatment. The summary statistics are n, mean, median, SD, minimum and maximum. With respect to the mean change from baseline, the 95% confidence interval will also be computed. Boxplots for change from baseline versus time by treatment for all time points will also be generated. Boxplots will display Day 28, Day 56 and Day 84 assessments.

Potentially Clinically Significant (PCS) vital signs will be summarized by parameter. The summary will indicate the number of subjects with PCS-low or PCS-high values by visit and treatment group. The criteria for identifying PCS abnormalities for vital signs are summarized in Table 15.8,9

Table 15: Criteria for Potentially Clinical Significant Vital Sign Abnormalities

		Criteria	
Parameter	Age	PCS Low	PCS High
Pulse	5 to 14 years	\leq 50 bpm at any time post dose.	\geq 140 bpm at any time post dose.
(beats/min)	15 to 18 years	\leq 50 bpm at any time post dose.	\geq 120 bpm at any time post dose.
	18 and above	\leq 50 bpm at any time post dose.	\geq 110 bpm at any time post dose.
	Any	Any \geq 15 bpm decrease from baseline at any time post dose.	Any \geq 15 bpm increase from baseline at any time post dose.
Systolic Blood	7 to 12 years	≤ 117 mm HG at any time post dose.	≥ 130 mm Hg at any time post dose.
Pressure (mm Hg)	13 to 17 years	≤ 120 mm HG at any time post dose.	≥ 144 mm Hg at any time post dose.
	18 and above	≤ 90 mm HG at any time post dose.	≥ 150 mm Hg at any time post dose.
	Any	Any \geq 20 mm Hg decrease from baseline at any time post dose.	Any \geq 20 mm Hg increase from baseline at any time post dose.
Diastolic Blood	7 to 12 years	≤ 75 mm HG at any time post dose.	≥ 86 mm Hg at any time post dose.
Pressure (mm Hg)	13 to 17 years	≤ 80 mm HG at any time post dose.	≥ 92 mm Hg at any time post dose.

		Criteria	
Parameter	Age	PCS Low	PCS High
	18 and above	≤ 50 mm HG at any time post dose.	≥ 100 mm Hg at any time post dose.
	Any	Any \geq 15 mm Hg decrease from baseline at any time post dose.	Any \geq 15 mm Hg increase from baseline at any time post dose.

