The Cardiff Acne Disability Index (CADI) was used to assess the quality of life in all subjects at Baseline (Day 1) and at Weeks 4, 8 and 12.

The investigator assessed efficacy by using an Investigator's Global Assessment scale (IGA 5-point scale) and by counting the number of inflammatory and non-inflammatory lesions on the face at Baseline and Weeks 4, 8, and 12.

Number of Subjects:

Approximately 150 subjects with facial acne vulgaris were randomized at 10 centers to ensure at least 120 subjects will complete the study.

Diagnosis and Criteria for Inclusion / Exclusion (see protocol section 5.1 and 5.2):

Inclusion Criteria:

- 1. Subject understood the study procedures, was willing to comply with the study procedures and required visits, and agreed to participate by giving written informed consent. Subjects under the legal age of consent provided written assent and had the written informed consent of their legal guardian.
- 2. Subject (or legal guardian) was willing to authorize use and disclosure of protected health information collected for the study.
- 3. Subject was at least 12 years of age.
 - a. At selected site(s), a total of approximately eight subjects 9-11 years of age were enrolled into the 2 arms of DFD-03 lotion group (active and vehicle).
- 4. Female subjects were required to have their menstrual period at the Baseline Visit (as reported by the subject), except for subjects using hormonal contraceptives that preclude menstrual periods, if the subject was premenarchal, was postmenopausal for at least 12 months prior to baseline, was surgically sterilized (i.e. tubal ligation) or if the subject was without a uterus and/or both ovaries.
- 5. A clinical diagnosis of facial acne vulgaris with a facial Investigator's Global Assessment (IGA) score of 2 (mild) to 3 (moderate) at Baseline.
 - a. At selected site(s), up to twelve subjects with acne lesions on the chest and/or back (including shoulders) in addition to those on the face had the option of treating their back and/or chest (including shoulders) in addition to their face.
- 6. Inflammatory lesion count (papules and pustules) of at least 20 on the face, including the nose, at Baseline.
 - a. This criteria was not applicable to the 9-11 years age group as long as subjects had an IGA score of 2 (mild) to 3 (moderate) at Baseline.
- 7. Non-inflammatory lesion count (closed and open comedones) of at least 25 on the face, including the nose, at Baseline.

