3. STUDY OBJECTIVES AND ENDPOINTS

3.1. Study Objectives

The objectives of this study were to determine the safety and local tolerability of DFD-03 (tazarotene) Lotion 0.1% and to compare it with Tazorac (tazarotene) 0.1% Cream in the topical treatment of acne vulgaris for 12 weeks.

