3.2.2. Secondary Endpoints

The secondary safety endpoints are:

- Vital Signs (blood pressure and pulse rate)
- Physical Examination Data

The secondary efficacy endpoints are:

- Proportion of Subjects with IGA Success at Weeks 4, 8 and 12. IGA success is defined as an IGA score of 0 (Clear) or 1 (Almost Clear) with at least a 2-grade reduction from baseline.
- Absolute Change from Baseline in Inflammatory Lesion Counts at Weeks 4, 8 and 12. The following location of lesions will be summarized separately: face and chest/back/shoulders.
- Absolute Change from Baseline in Non-Inflammatory Lesion Counts at Weeks 4, 8 and 12. The following location of lesions will be summarized separately: face and chest/back/shoulders.
- Percent Change from Baseline in Inflammatory Lesion Counts at Weeks 4, 8 and 12. The following location of lesions will be summarized separately: face and chest/back/shoulders.
- Percent Change from Baseline in Non-Inflammatory Lesion Counts at Weeks 4, 8 and 12. The following location of lesions will be summarized separately: face and chest/back/shoulders.
- Change from Baseline in Cardiff Acne Disability Index (CADI) at Weeks 4, 8 and 12. The following location of lesions will be summarized separately: face and chest/back/shoulders.

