4.4. Randomization

Subjects were assigned randomly to one of the four treatment arms, DFD-03 (tazarotene) Lotion 0.1%, Tazorac (tazarotene) Cream, 0.1%, Vehicle Lotion or Vehicle Cream in a 2:2:1:1 ratio (50 subjects each to DFD-03 Lotion and Tazorac Cream, and 25 subjects each to Vehicle Lotion and Vehicle Cream). A treatment assignment schedule was created with kit numbers randomly assigned to study products. The date and time of randomization and the bottle/tube number should have been entered on the eCRF.

[name], Ltd Statistical Analysis Plan, Version 2.0

For the selected site(s) enrolling subjects in the 9-11 age group, subjects were assigned randomly to one of the two treatment arms, DFD-03 (tazarotene) Lotion 0.1%, and 0.1%, Vehicle Lotion in a 1:1 ratio (4 subjects each to DFD-03 Lotion and Vehicle Lotion). A treatment assignment schedule was created with kit numbers randomly assigned to study products, which is independent from the treatment assignment schedule created for ages 12 and older.

For the selected site(s) enrolling subjects with acne involvement on the face, chest and/or back including shoulders, subjects were assigned randomly to treatment with either DFD-03 (tazarotene) Lotion 0.1%, Tazorac (tazarotene) Cream, 0.1%, Vehicle Lotion or Vehicle Cream in a 2:2:1:1 ratio. Since these subjects were treating their face, chest and/or back and shoulders, the subject kit size contained more study medication for application. A treatment assignment schedule was created for these larger kit sizes with kit numbers randomly assigned to study products, which is independent from the treatment assignment schedules created for ages 9-11 and 12 and older.

A unique subject number was assigned to each subject. The randomization number (kit number) was designated as the subject number. The subject maintained the same subject number and treatment assignment throughout the study. Subject numbers were assigned immediately prior to dispensing study medication and were assigned starting with the lowest available number at the study site.

The Investigator designated an independent third party study medication dispenser who dispensed to qualified subjects, collected all bottles/tubes of study product and dispensed and collected diaries.

No stratification based on age or other characteristics was performed.

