6.4. Data Presentation Conventions

Continuous variables (e.g. age) are summarized using descriptive statistics (the number of subjects with available data, the mean, standard deviation (SD), median and minimum and maximum). Categorical variables (e.g. race) are summarized using counts and percentages. Percentages are calculated using the total subjects per treatment group.

The following conventions are applied to all data presentations and summaries.

For continuous variables, all mean and median values are formatted to one more decimal place than the measured value. Standard deviation values are formatted to two more decimal places than the measured value. Minimum and maximum values are presented with the same number of decimal places as the measured value.

For categorical variables, the number and percentage of responses are presented in the form XX (XX.X %) where the percentage is in the parentheses.

Date variables are formatted as DDMMMYYYY for presentation. Time is formatted in military time as HH:MM for presentation.

Wherever possible, data will be decimal aligned.

P-values, if applicable, will be presented to 4 decimal places. If the p-value is less than 0.0001 then it will be presented as <0.0001.

Unless otherwise stated, any statistical tests performed will use 2-sided tests at the 5% significance level.

The table and listing shells and table of contents as part of this SAP provide the expected layout and titles of the tables, listings and figures. Any changes to format, layout, titles, numbering, or any other minor deviation will not necessitate a revision to the SAP nor will it be considered a deviation from planned analyses. Only true differences in the analysis methods or data handling will necessitate such documentation. The appropriate listings supporting the tables will be included and are not specified in the individual sections throughout the document.

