6.7.3. Change from Baseline

Change from baseline is calculated as (post-baseline result – baseline result). Data will not be imputed for a specific post-baseline time point if the data was not recorded. Changes from baseline will be calculated based on the matched pairs of data points (subjects with data at both baseline and post-baseline).

Percent change from baseline is calculated as (change from baseline/baseline result * 100).

If either the baseline or the post-baseline result is missing, the change from baseline and/or percentage change from baseline will be set to missing.

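### The only confidence interval planned for vital signs is each arm's own change from baseline; no interval is planned for a difference between randomised arms, so drug effect and shared drift cannot be told apart from it

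*SAP*

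**What the plan says.** Blood pressure and pulse rate are a secondary safety endpoint (SAP 3.2.2). For change in these parameters SAP 9.6 says "Changes from baseline will also be summarized by visit and treatment", lists n, mean, median, SD, minimum and maximum, and adds: "With respect to the mean change from baseline, the 95% confidence interval will also be computed". SAP 6.7.3 defines change as the post-baseline result minus the same subject's baseline, so no control arm enters the calculation.

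This is the only confidence interval named in either document. Tolerability scores get counts and percentages (SAP 9.2), adverse events get counts (SAP 9.3.4), and efficacy gets descriptive statistics (SAP 8.3). SAP 6.4 has a general convention, "Unless otherwise stated, any statistical tests performed will use 2-sided tests at the 5% significance level", but no between-arm test or interval is specified for vital signs.

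The objectives in SAP 3.1 are to determine the safety and local tolerability of DFD-03 and "to compare it with Tazorac (tazarotene) 0.1% Cream in the topical treatment of acne vulgaris for 12 weeks". Planned arm sizes in SAP 4.4 are "50 subjects each to DFD-03 Lotion and Tazorac Cream, and 25 subjects each to Vehicle Lotion and Vehicle Cream". The vital-signs shell (Table 14.3.3 in the SAP's display index, labelled 14.3.4 in the layouts) has rows for n, mean (SD), median and range only. The interval promised in 9.6 has no row there.

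**The concern.** A one-arm interval for change from Day 1 shows whether that arm moved. It does not show whether the product moved it. Anything that shifts all arms alike, such as settling after early visits, regression to the mean or season, shifts every interval. The randomised comparison would cancel that shared movement, and it is not calculated.

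The 2:2:1:1 allocation adds an asymmetry: active-arm intervals are narrower than vehicle intervals, so the same shared movement is more likely to clear zero in an active arm than in its own vehicle. Set side by side, such a pair can look like a systemic effect on blood pressure or pulse when the arms do not differ. The two active arms can also appear to disagree by chance. What is at stake is the reading of a secondary safety endpoint; the primary tolerability data do not depend on this interval.

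**Working it through.** **Arm sizes.** 150 × 2/6 = 50 and 150 × 1/6 = 25, which reproduces the SAP's 50/50/25/25. The SAP's opening summary says "Approximately 150 subjects with facial acne vulgaris were randomized at 10 centers to ensure at least 120 subjects will complete the study". That is a loss of 1 − 120/150 = 20%, leaving 40/40/20/20 completers. If the 8 subjects aged 9-11 sit inside the 150 and go 1:1 to the lotion arms, expected sizes in the order DFD-03, Tazorac, Vehicle Lotion, Vehicle Cream are 142 × (2, 2, 1, 1)/6 + (4, 0, 4, 0) = 51.3, 47.3, 27.7, 23.7. The direction of what follows is unchanged.

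**Interval width.** The half-width is t(0.975, n−1)/√n, in units of the SD of change: 0.284 at n = 50 and 0.413 at n = 25. The ratio is 0.284/0.413 = 0.69, so the active interval is about 30% narrower.

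**How often it excludes zero.** Assume the same drift in every arm and no treatment effect, and write δ = drift/SD. The probability that a one-sample 95% t-interval excludes zero follows from the noncentral t distribution with n − 1 degrees of freedom and noncentrality δ√n. For an independent active and vehicle arm, the chance that only the active interval excludes zero is p50 × (1 − p25); the reverse is p25 × (1 − p50).

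| δ | n = 50 | n = 25 | active only | vehicle only |
|---|---|---|---|---|
| 0 | 5.0% | 5.0% | 4.8% | 4.8% |
| 0.1 | 10.7% | 7.7% | 9.8% | 6.9% |
| 0.2 | 28.4% | 16.1% | 23.8% | 11.5% |
| 0.3 | 54.8% | 30.2% | 38.2% | 13.7% |
| 0.4 | 79.2% | 48.4% | 40.9% | 10.1% |
| 0.5 | 93.4% | 67.0% | 30.8% | 4.4% |

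The active-only pattern is not monotone: it falls again once drift is large enough for both intervals to exclude zero. The two active arms disagree with probability 2 × p50 × (1 − p50): 2 × 0.284 × 0.716 = 41% at δ = 0.2, and 2 × 0.548 × 0.452 = 50% at δ = 0.3. With completers only (40 and 20), δ = 0.3 gives 45.7% against 24.7%.

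**In units.** The documents give no SD or drift. Assuming an SD of change of 8 to 12 (mmHg or bpm) and a shared drift of 2 to 3 units, the active interval excludes zero in 21% to 74% of trials and the vehicle interval in 13% to 44%. At a drift of 1 unit the active rate is 9% to 14%.

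**The between-arm interval.** Two-sample 95% t-intervals were simulated under shared drift of 0.2 to 0.5 SD (100,000 runs for 50 v 25; 50,000 for 50 v 50). They excluded zero in 4.9% to 5.1% of runs at every drift. Half-widths before baseline adjustment are t(0.975, 98) × √(2/50) = 0.397 SD for active v active, and t(0.975, 73) × √(1/50 + 1/25) = 0.488 SD for active v vehicle. Against 0.284 these are 1.4 and 1.7 times as wide.

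**Number of intervals.** Planned: 3 parameters × 3 visits × 4 arms = 36, of which 36 × 0.05 = 1.8 would exclude zero by chance with no drift. Three between-arm contrasts would give 3 × 3 × 3 = 27, or 27 × 0.05 = 1.35.

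**The case against.** The best reply is that nothing in the plan turns on this interval. No test, threshold or conclusion is attached to it, Protocol 11.5.5 asks only for descriptive statistics, and SAP 4.3 says the study is not powered for significance. The shell sets the four arms in adjacent columns, so similar mean changes would be visible, and the tabulated n, mean and SD let anyone calculate an unadjusted difference interval by hand. The objective has two parts, and a within-arm interval is a legitimate precision statement for the first, describing DFD-03's safety. SAP 9.6 also counts individual changes of at least 20 mmHg systolic, 15 mmHg diastolic or 15 bpm, far above the drifts assumed here. The drift may be small: eligibility limits are broad, and when Screening is a separate visit the baseline reading is not the first one.

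All of that stands, and it rules out three stronger readings. A reader might infer that shared drift will be reported as a drug effect; the judging against zero is the reader's, since the SAP sets no such rule. A reader might infer that the within-arm interval is wrong and should go; it is valid for what it measures. A reader might infer that the primary comparison is compromised; vital signs are secondary and the tolerability analysis does not use this interval.

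None of it supplies the missing estimate. Adjacent means carry no stated uncertainty for their difference, hand calculation is not a plan, and counts of large individual changes do not estimate a difference in mean change.

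**Conclusion.** The point holds as a limited gap in estimation. SAP 9.6 plans intervals for change within each arm and none for a difference between randomised arms, so they cannot distinguish a drug effect from shared change. That conclusion rests on the text alone.

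The size of any misreading rests on assumptions: normal changes, equal SD, identical drift in all arms, and a reader who compares intervals with zero. The unequal allocation matters only if drift is non-zero; with none, both arm sizes give 5%, and at very large drift both approach 100%. Multiplicity is not a reason for the change, since the expected number of chance exclusions falls only from 1.8 to 1.35. The missing interval row in the shell is a separate mismatch within the SAP that needs correcting whichever interval is kept. This is a desirable improvement and does not threaten the study's main result.

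**What to change.** Add to SAP 9.6:

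> For each vital-sign parameter and post-baseline visit, the between-arm difference in mean change, adjusted for the baseline value, will be presented with a 95% confidence interval for DFD-03 Lotion minus Tazorac Cream, DFD-03 Lotion minus Vehicle Lotion, and Tazorac Cream minus Vehicle Cream. These intervals are descriptive.

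Compute all three in subjects aged 12 and older, or adjust the lotion contrast for cohort. Subjects aged 9-11 were randomised on a separate schedule, 1:1 and to the lotion arms only, so an unadjusted lotion contrast would pool a 1:1 cohort with a 2:1 cohort, and the Tazorac contrast would compare different age mixes.

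Within-arm intervals may stay if the sponsor wants them, labelled as descriptive and not as estimates of drug effect. Add interval rows to the vital-signs shell for whatever is kept.

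The cost is a few sentences and table rows, with no new data, subjects or procedures. The difference intervals are about 1.4 times (active v active) and 1.7 times (active v vehicle) as wide as the active-arm interval before baseline adjustment. Restricting the lotion contrast to ages 12 and older widens it by about 7% compared with including the 8 younger subjects: √[(1/47.3 + 1/23.7)/(1/51.3 + 1/27.7)] = 1.07.

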  - Diastolic BP < 100 and > 50 mmHg
  - Pulse 50 to 100 bpm inclusive for adults; up to 110 bpm for subjects < 18 years of age;

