## 7.10.6 Unscheduled Visit (If Applicable)

### Conduct the following, as needed.

- 1. Evaluate treatment and protocol compliance and record any deviations.
- 2. Collect vital signs (blood pressure and pulse).
- 3. Collect AE data. This includes a review of the diary card for potential AEs.
- 4. Update concomitant medications data.
- 5. The independent third party study medication dispenser will weigh and then dispense/re-dispense, collect and weigh study product, as needed.
- 6. Conduct a urine pregnancy test for all females.
- 7. Complete eCRF.

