- 11. Subjects were willing to comply with sun avoidance measures for the face (as well as back/chest and shoulders, if applicable) including use of investigator-approved sunscreen and/or hats, had limited sun exposure time, and had no tanning bed use.
- 12. Subject must have been in good general health as determined by the investigator and supported by the medical history, physical examination, and normal or not clinically significant abnormal vital signs (blood pressure and pulse). Subjects were eligible if:
 - a. Systolic blood pressure (BP) < 160 and > 85 mmHg
 - b. Diastolic BP < 100 and > 50 mmHg
 - c. Pulse 50 to 100 bpm inclusive for adults; up to 110 bpm for subjects < 18 years of age

Exclusion Criteria:

- 1. Females who were pregnant or lactating or planning to become pregnant during the study period.
- 2. Treatment with the following products:
 - a. Topical acne treatments (retinoids, antibiotics, benzoyl peroxide, azelaic acid, resorcinol, salicylates, α-hydroxy/glycolic acid), or other topical facial medication (antifungals, steroids, anti-inflammatories) on the treatment area in the 14 days prior to the Baseline Visit, including prescription and non-prescription products.
 - b. Systemic corticosteroids, systemic acne treatments including systemic antibiotics used for treatment of acne, potential photosensitizing agents (thiazides, phenothiazines), spironolactone, flutamide, or immunosuppressant drugs in the 30 days prior to the Baseline Visit.
 - c. Systemic retinoid use (including high dose vitamin A > 10,000 units per day) in the 180 days prior to the Baseline Visit.
 - d. Undertaken certain facial procedures such as chemical peel, laser treatment, photodynamic therapy, acne surgery, cryodestruction or chemodestruction, x-ray therapy, intralesional steroids, dermabrasion, or depilation (except eyebrow shaping) in the 30 days prior to the

[name], Ltd Statistical Analysis Plan, Version 2.0

Baseline Visit. After the subject is enrolled in the study, eyebrow shaping (except for tweezing) is prohibited.

- e. Treatment with a medication or procedure that, in the opinion of the investigator, would put the subject at unacceptable risk for participation in the study or may interfere with evaluations in the study.
- f. Treatment with an investigational product or device in the 30 days prior to the Baseline Visit.

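### SAP 9.6 counts vital signs beyond Table 15's absolute limits without reference to baseline, although inclusion criterion 12 admits values already beyond several of them, most of all in minors

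*SAP*

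**What the plan says.** Vital signs are a secondary safety endpoint (SAP 3.2.2). For the PCS display SAP 9.6 states: "The summary will indicate the number of subjects with PCS-low or PCS-high values by visit and treatment group". Table 15 then gives two kinds of row.

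- Age-specific rows with absolute limits. Adult systolic PCS High is "≥ 150 mm Hg at any time post dose". Systolic PCS Low is "≤ 117 mm HG at any time post dose" at 7 to 12 years and "≤ 120 mm HG at any time post dose" at 13 to 17 years.
- Rows for any age that flag a change from baseline of at least 15 bpm, 20 mmHg systolic or 15 mmHg diastolic.

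No text makes an absolute flag depend on the baseline value, and none says whether the two kinds of row combine by OR or by AND. SAP 6.7.5 takes the worst result of a visit for abnormality tables. The list of displays in SAP 11.2 has a table of vital-sign results and change from baseline, but no PCS table and no shift table, so no shell settles the rule.

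Inclusion criterion 12 (Protocol 5.2, repeated in the SAP's Technical Summary Report) sets the entry ranges: "Systolic blood pressure (BP) < 160 and > 85 mmHg", "Diastolic BP < 100 and > 50 mmHg" and "Pulse 50 to 100 bpm inclusive for adults; up to 110 bpm for subjects < 18 years of age".

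**The concern.** The entry ranges and the absolute limits were evidently set independently, and they overlap. An adult enrolled at 155 mmHg who stays at 155 is PCS High at Weeks 4, 8 and 12, and nothing in the display shows that the value was there before dosing.

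The SAP takes care of this elsewhere. A treatment-emergent adverse event must start or worsen after first dose (SAP 9.3.1.2), and local tolerability has a second summary without subjects who had signs at baseline (SAP 9.2). The PCS count has no such safeguard.

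At stake is the meaning of the count. A reader will take it as abnormality arising on treatment, when part of it, and in minors probably most of it, would be enrolment values carried forward.

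Two smaller gaps sit in the same section. Age 18 falls in two pulse bands. The limits are worded to apply at any time after dosing, but the count is by visit, so unscheduled readings outside the visit windows have no row.

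**Working it through.** The plan states no expected PCS count, so there is no figure to reproduce.

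**Step 1: overlap.** In whole units, criterion 12 admits systolic 86-159 (159 − 86 + 1 = 74 values), diastolic 51-99 (49 values), and pulse 50-100 for adults, up to 110 under 18. The lower pulse limit of 50 is stated for adults only; I assume it for minors too. A value is counted below if it is admissible and already meets the absolute limit, so that a subject with no change is flagged.

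| Row of Table 15 | PCS Low / High | Admissible and already flagged | Count |
|---|---|---|---|
| Systolic, 18 and above | ≤ 90 / ≥ 150 | 86-90, 150-159 | 5 + 10 = 15 of 74 |
| Systolic, 13-17 | ≤ 120 / ≥ 144 | 86-120, 144-159 | 35 + 16 = 51 of 74 |
| Systolic, 7-12 | ≤ 117 / ≥ 130 | 86-117, 130-159 | 32 + 30 = 62 of 74 |
| Diastolic, 18 and above | ≤ 50 / ≥ 100 | none | 0 of 49 |
| Diastolic, 13-17 | ≤ 80 / ≥ 92 | 51-80, 92-99 | 30 + 8 = 38 of 49 |
| Diastolic, 7-12 | ≤ 75 / ≥ 86 | 51-75, 86-99 | 25 + 14 = 39 of 49 |
| Pulse, every age row | ≤ 50 / ≥ 110, 120 or 140 | 50 only | 1 value, low side |

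These are counts of possible values, not of subjects.

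**Step 2: share of subjects, under assumptions.** The documents give no baseline distribution. I take a normal distribution truncated to the admissible range, with continuity correction, F being its cumulative function.

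Adult share = {[F(90.5) − F(85.5)] + [F(159.5) − F(149.5)]} / [F(159.5) − F(85.5)]

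- Mean 120, SD 11: 0.28% low + 0.35% high = 0.63%.
- Mean 110, SD 13: 3.82% low + 0.12% high = 3.94%.

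These are the extremes over means 110-120 and SDs 11-13. In an active arm of 50, if all were adults, that is 50 × 0.0063 = 0.3 to 50 × 0.0394 = 2.0 subjects. The part at 150-159 alone is 0.02% to 1.05%.

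The same formula for systolic at 13-17 years (cut-offs 120.5 and 143.5):

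- Mean 120, SD 10: 52.0% low + 0.9% high = 52.9%.
- Mean 105, SD 10: 93.8% low + 0.0% high = 93.8%.

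These are the extremes over means 105-120 and SDs of 10 or 12. Almost all of it is PCS Low. The trial enrols from age 12, plus about eight subjects aged 9-11, but gives no expected age mix, so I do not convert this to a number per arm.

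**Step 3: age 18 in the pulse rows.** One band runs from 15 to 18 years (PCS High ≥ 120) and the next starts at 18 (≥ 110). An 18-year-old at 110-119 bpm meets one limit and not the other. The change row settles most of this: with an admissible baseline of at most 100, any reading of 115 or more is a rise of at least 15 and is PCS High anyway. A reading stays ambiguous only if it is at least 110 and less than 15 above baseline, which needs a baseline of 96-100 and a reading of 110-114.

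**Step 4: readings outside visits.** Protocol 7.10.6 provides for vital signs at unscheduled visits. SAP 6.7.4 defines windows for Days 25-31, 51-61 and 79-89 only. The rule that assigns termination-visit data to a scheduled visit (SAP 8.3) covers efficacy data. A post-dose reading outside the windows therefore has no defined place in a by-visit PCS count.

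**The case against.** The strongest reply is that baseline is not ignored. Table 15 has change-from-baseline rows, SAP 9.6 also plans baseline values, changes with 95% confidence intervals and boxplots, and the vital-signs listing shows every visit, so a stable 155 can be recognised as stable. That is true, but none of it changes the PCS count or shows how much of it was present before dosing. If absolute and change rows were meant to combine by AND, unchanged values would not be flagged; the layout, with any age as a separate row, reads as OR, and the SAP would have to say otherwise.

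Three stronger readings are tempting and are not supported.

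- *One product could be made to look worse.* Randomisation balances subjects beyond a limit at baseline in expectation, so there is no systematic bias between arms. The study is descriptive and not powered (SAP 4.3). Chance imbalance in small arms remains possible.
- *Problems between visits are lost.* Protocol 8.2 has clinically significant vital signs after Visit 2 reported as adverse events, and TEAEs are a primary endpoint. Extra readings within a visit enter through the worst-result rule. Only the PCS tabulation of other readings is undefined.
- *The whole table conflicts with eligibility.* Adult diastolic and every pulse-high limit are free of overlap.

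A fair objection also applies to the obvious remedy. Counting only subjects newly beyond a limit hides worsening: an adult going from 151 to 165 mmHg (+14) is not newly beyond 150 and does not reach the 20 mmHg change.

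**Conclusion.** The point holds as a minor but real defect in a secondary safety display. Followed as written, with the rows read as OR, SAP 9.6 reports unchanged enrolment values as post-dose PCS for systolic pressure at all ages, diastolic pressure under 18, and a pulse of exactly 50.

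The size depends on assumed distributions. In adults it is small. At 13-17 years it covers at least about half of subjects on systolic pressure alone under the values tried, so the low-side count there would say little about treatment. The paediatric rows of Table 15 and criterion 12 do not fit together and must be reconciled by the sponsor; I take no view on which limits are right. The age-18 overlap and the missing row for other readings are small. What suffers is the absolute counts and their interpretation.

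**What to change.** In SAP 9.6, before database lock:

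1. For each absolute limit, show by arm the number of subjects beyond it at baseline and a baseline-by-post-baseline shift (low, normal, high). Report the number newly beyond the limit next to the all-subject count, so that worsening in subjects already beyond it at baseline stays visible. An unchanged value then no longer counts as new in any row.
2. State that absolute and change-from-baseline rows are separate criteria (OR), and tabulate them separately.
3. Make the pulse age bands exclusive, so that age 18 falls in one band, as the blood-pressure rows already do.
4. Add one any-post-baseline row per arm that includes unscheduled and early-termination readings and counts each subject once.
5. Have the sponsor reconcile the paediatric rows with criterion 12, and add the PCS table to the list of displays.

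Items 1 to 4 cost SAP wording, some programming and a slightly larger table. They need no new data and no change to any limit.
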